Abbreviations: eval = evaluation; O.P. = observation period; Tx = treatment.

a – Administer IMC-CS4; b – Observation period; c – Radiographic assessment of tumor status; d – Baseline assessment, within 28 days prior to the first dose of study therapy; subsequent assessment should be performed in the week prior to the onset of the new cycle.

Table 3. Treatment Schedule (Part A - Every-2-Week Dosing – Cohort 4)

Week	1	2	3	4	5	6	7	8	9	10	11	12	13	14	15	16	17	18	19	20	21	22	23	24
	Cycle 1						Cycle 2						Cycle 3						Cycle 4					
Tx ^a	X		X				X		X		X		X		X		X		X		X		X	
O.P. ^b				X	X	X																		
Tumor eval ^c	X ^d				X					X							X							X

Abbreviations: eval = evaluation; O.P. = observation period; Tx = treatment.

a – Administer IMC-CS4; b – Observation period; c – Radiographic assessment of tumor status; d – Baseline assessment, within 28 days prior to the first dose of study therapy; subsequent assessment should be performed in the week prior to the onset of the new cycle.

Table 4. Treatment Schedule (Part B - Weekly Dosing – Cohorts 6a, 6c, 7a, 7c, 8a, and 8c)

Week	1	2	3	4	5	6	7	8	9	10	11	12	13	14	15	16	17	18	19	20	21	22	23	24
	Cycle 1						Cycle 2						Cycle 3						Cycle 4					
Tx ^a	X	X	X	X	X	X	X	X	X	X	X	X	X	X	X	X	X	X	X	X	X	X	X	X
O.P. ^b																								
Tumor eval ^c	X ^d					X					X						X							X

Abbreviations: eval = evaluation; O.P. = observation period; Tx = treatment.

a – Administer IMC-CS4; b – Observation period; c – Radiographic assessment of tumor status; d – Baseline assessment, within 28 days prior to the first dose of study therapy; subsequent assessment should be performed in the week prior to the onset of the new cycle.

Table 5. Treatment Schedule (Part B - Weekly Dosing on Weeks 1, 2, 4, and 5 – Cohorts 6b, 7b, and 8b)

Week	1	2	3	4	5	6	7	8	9	10	11	12	13	14	15	16	17	18	19	20	21	22	23	24
	Cycle 1						Cycle 2						Cycle 3						Cycle 4					
Tx ^a	X	X		X	X		X	X		X	X		X	X		X	X		X	X		X	X	
O.P. ^b																								
Tumor eval ^c	X ^d					X					X						X							X

Abbreviations: eval = evaluation; O.P. = observation period; Tx = treatment.

a – Administer IMC-CS4; b – Observation period; c – Radiographic assessment of tumor status; d – Baseline assessment, within 28 days prior to the first dose of study therapy; subsequent assessment to be performed in the week prior to the onset of the new cycle.

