5.2.2 Efficacy Data Handling and Definitions

Study evaluations will take place in accordance with the flow chart in Section 7.6 of the CP24-1001 Study Protocol.

Subjects will be evaluated for response according to RECIST 1.1 guidelines.^[i] Subjects will be evaluated for response every 6 weeks (± 3 days) following the first dose of study therapy until radiographic documentation of PD, even if therapy is delayed due to toxicity or for other reasons.

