5.2.2.1 Determination of Best Overall Response (BOR)

The Best Overall Response (BOR) will be determined using the RECIST (Version 1.1) guidelines. It is defined as the best response across all time points from the start of the treatment until disease progression based on investigators assessment. When SD is believed to be best overall response, it needs to be assessed a minimum of 39 days (ie, 6 weeks – 3 days as allowed per protocol) after start of treatment. Otherwise, the best overall response will be NE, unless any PD was further documented, in which case BOR will be PD. Tumor response (ie, for complete response [CR] or partial response [PR]) will not be confirmed following initial documentation of objective response.

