5.3.3.1 Response

Best overall response rate (number of subjects who achieve a best response of CR or PR during therapy divided by the total number of subjects treated) and disease control rate (number of subjects who achieve a best response of CR or PR or SD during therapy divided by the total number of subjects treated) will be presented for each cohort of subjects and overall. In addition all tumor assessments will be included in patient listings.

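### The SAP's 39-day minimum for stable disease rests on a scan window the current protocol does not contain, so some on-schedule stable scans do not count and the disease control rate can only be lowered

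*SAP*

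**What the plan says.** **SAP.** Section 5.2.2.1 defines best overall response as the "best response across all time points from the start of the treatment until disease progression", on the investigator's assessment. For SD to be that best response, "it needs to be assessed a minimum of 39 days" after the start of treatment, which the SAP explains as 6 weeks less 3 days permitted by the protocol. If the test is failed: "Otherwise, the best overall response will be NE, unless any PD was further documented, in which case BOR will be PD". The 3 days match the schedule in SAP 5.2.2: "Subjects will be evaluated for response every 6 weeks", with a margin of 3 days either side, "following the first dose of study therapy until radiographic documentation of PD, even if therapy is delayed". The same section also says that evaluations follow the flow chart in protocol Section 7.6. SAP 5.3.3.1 reports the "disease control rate (number of subjects who achieve a best response of CR or PR or SD during therapy", divided by all subjects treated, for each cohort and overall. SAP 3.1 states that the plan was written for protocol Version 3.0 of 28 March 2012.

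**Protocol Version 7.0.** One cycle is 6 weeks (Section 4.1). Footnote d of Tables 2 to 4 says of scans after baseline: "subsequent assessment should be performed in the week prior to the onset of the new cycle"; Table 5 has the equivalent. Section 6.7 puts the end-of-Cycle-1 tumor evaluation in the same week. Table 6, footnote p, wants the scan done before a cycle starts so that the result is known before dosing. Footnote a gives visit windows of ± 2 days for the weekly cohorts and Cohorts 6b, 7b and 8b, and ± 3 days for every-2-week cohorts, of which only Cohort 4 remains.

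**The concern.** The only reason the SAP gives for 39 days is that it is the earliest day on which a scan could be on time. It is not presented as a minimum duration of clinical benefit. The number therefore has to match the scan window that sites actually follow, and under the current protocol it falls inside that window instead of at its opening.

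Take a subject scanned on time at day 36 with SD who progresses at the Week 12 scan. The SAP reports PD. A similar subject with no further scan is reported as NE. Both leave the numerator of the disease control rate and stay in its denominator. The result then depends partly on which day of the week a site books the scan. Cohorts here are commonly 3 to 6 subjects, so one such case moves a cohort's rate by 1/6 to 1/3, that is 17 to 33 percentage points.

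**Working it through.** Days below are elapsed days after first dose (first dose = day 0).

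1. **Reproduce the SAP's figure.** 6 × 7 − 3 = 39. The SAP's own window is 42 ± 3, or days 39 to 45, and the minimum sits at its lower edge. The SAP is internally consistent.

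2. **Protocol scan week.** With Cycle 2 starting on day 6 × 7 = 42, the preceding week is 42 − 7 = 35 to 42 − 1 = 41. This uses the footnote and text, not the position of the marks in Tables 2 to 5.

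3. **Day-count convention.** SAP 5.2.3 defines a duration in days as End − Start + 1. SAP 5.2.2.1 does not say whether that applies to the 39 days. If it does, an elapsed 38 days qualifies.

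4. **Scan days that fail.**

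| First-scan window | Days | Fail, elapsed count | Fail, +1 count |
|---|---|---|---|
| SAP, 42 ± 3 | 39–45 | 0/7 | 0/7 |
| Protocol, Cycle 2 on day 42 | 35–41 | 4/7 = 57% | 3/7 = 43% |
| Same, also allowing a pre-dose scan on Cycle 2 Day 1 | 35–42 | 4/8 = 50% | 3/8 = 38% |
| Protocol, Cycle 2 two days early | 33–39 | 6/7 = 86% | 5/7 = 71% |
| Protocol, Cycle 2 two days late | 37–43 | 2/7 = 29% | 1/7 = 14% |

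   Reading these as shares of subjects assumes that scans are spread evenly over the window. The documents do not say so.

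5. **From failing scan to changed best response.** Best response is taken over all time points to progression. The second scan falls nominally on days 84 − 7 = 77 to 84 − 1 = 83, and SD there qualifies. So:

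   share of first-scan SD subjects recoded = (share scanned too early) × (share of those with no later SD, PR or CR).

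   The second factor is not in the documents. Assuming 25%, 50% or 75%:
   - 25%: 3/7 × 0.25 = 11% to 4/7 × 0.25 = 14%
   - 50%: 21% to 29%
   - 75%: 32% to 43%

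6. **Effect on the disease control rate.** Loss = (share with SD at first scan) × (share recoded). Assuming 20% to 40% have SD at the first scan, the loss runs from 0.20 × 3/7 × 0.25 = 2 points to 0.40 × 4/7 × 0.75 = 17 points. In a group the size of Part A (about 30 subjects, protocol 12.1), that is about 0.6 to 5 subjects.

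7. **Direction.** Compared with counting every on-schedule SD scan, the rule only removes SD. It never adds SD, PR or CR.

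**The case against.** A reader might infer that most on-schedule stable scans are recoded to NE or PD. The documents do not support that. A failing first scan changes nothing if a later scan shows SD, PR or CR before progression. For a majority of first-scan SD subjects to be recoded under the 4/7 count, more than 0.5 ÷ (4/7) = 87.5% of those scanned early would need to have no later qualifying scan. Under the 3/7 count a majority is impossible in the nominal window with evenly spread scans.

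A reader might also infer an arithmetic slip or a poor choice of rule. That is not shown either. Against its own window no scan day fails, and the SAP attributes the 3 days to protocol Version 3.0, which is not among the documents. The window may have been right then. This explains the mismatch with Version 7.0 but does not remove it. SAP 5.2.2 also defers to the protocol flow chart, which in the current version calls for pre-cycle scans.

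Three mitigations stand:
- Protocol 7.3 asks for every effort to scan at 6 and 12 weeks after first dose in subjects who stop for reasons other than PD. A scan at day 42 passes, and so does SD at 12 weeks.
- A delayed Cycle 2 moves the pre-cycle scan later, often past day 39.
- Tumor measurements, scans and best response are listed by patient (SAP 6.4, Listings 13.1 to 13.6), so a recoded case can be traced.

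The consequence is also limited. Antitumor activity is exploratory (protocol 2.3), Section 12.6 of the current protocol no longer names a disease control rate, and the RP2D rests on the DLT population (12.2).

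**Conclusion.** The mismatch is real and should be corrected, with limited consequences. Under protocol Version 7.0, an on-schedule SD scan on days 35 to 38 (elapsed count) or 35 to 37 (+1 count) fails the SAP minimum. Those affected are subjects scanned on those days who have no later SD, PR or CR before progression, and the bias in the disease control rate runs downward only.

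Its size cannot be fixed from the documents. The illustrative loss of 2 to 17 points rests on an even spread of scans, Cycle 2 starting on day 42, 20% to 40% SD at the first scan, and 25% to 75% of early-scanned SD subjects having no later qualifying scan. All of these except the nominal Cycle 2 day are assumptions. Dose escalation and RP2D determination are not touched.

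**What to change.** In SAP 5.2.2.1, replace 39 days with the opening of the protocol's first scan week: 35 elapsed days after first dose, at which 0 of the 7 nominal scan days fail. If early Cycle 2 visits within the allowed window are to be honoured, the week opens at 40 − 7 = 33 days for the ± 2-day cohorts and 39 − 7 = 32 days for every-2-week Cohort 4. A single value of 33 would still reject compliant Cohort 4 scans. Alternatively, drop the fixed number and let SD count from the scheduled end-of-Cycle-1 scan.

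State whether the count is elapsed days or End − Start + 1. Rewrite the schedule sentence in SAP 5.2.2 to follow the protocol's end-of-cycle scans, and cite the current protocol version.

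The cost is one threshold and two sentences in the SAP. It needs no new data and no change for subjects or sites.

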5.2.3 General Data Handling

- **Continuous variables** will be summarized using descriptive statistics, ie, number of non-missing records (n), mean, median, standard deviation, minimum, and maximum.
- **Categorical variables** will be summarized by frequency and its corresponding percentage.
- **Missing Data:** All analyses and descriptive summaries will be based on the observed data. Unless otherwise specified, missing data will not be imputed or “carried forward.”
- **Baseline Measurement:** Unless otherwise specified, the last valid (ie, non-missing) measurement prior to the first dose of study medication will serve as the baseline measurement.
- **Date of Birth:** CRF records only the year of birth. For analysis purposes, July 1 will be used as the month and day of birth
- **Age (years)** = (Date of informed consent – Date of birth + 1) / 365.25
- **Duration:** Duration is calculated as:
 - Duration (days) = (End Date – Start Date + 1)
 - Duration (weeks) = (End Date – Start Date + 1) / 7

- Duration (months) = $(\text{End Date} - \text{Start Date} + 1) / 30.4375^4$
- Duration (years) = $(\text{End Date} - \text{Start Date} + 1) / 365.25^5$

5.3 Data analysis

5.3.1 Disposition of Patients

The number of patients enrolled and the number of screening failures will be presented.

Number (percent) of patients who were in the Safety population and in the ~~MTD-DLT~~ population, discontinued treatment and discontinued study as of data cut-off date will be summarized. A patient will be considered as off treatment if the End of Treatment form has been completed. A patient will be considered as off study if the End of Study visit has been completed or withdrew consent (ie, discontinued treatment due “withdrawal of consent” according to the End of Treatment form). Number (percent) of patients who discontinued will also be summarized by reason for discontinuation. A listing of patients with protocol deviations will be provided.

5.3.2 Demographic and Baseline Characteristics

The following demographic and baseline characteristics will be summarized using the Safety population:

Demographic:

- Age (years) and age categories (<65 years vs. ≥ 65 years)
- Gender
- Race and Ethnicity
- Height (cm)
- Weight (kg)
- Eastern Cooperative Oncology Group (ECOG) performance status

⁴Days in months = average number of days in a year / 12.

⁵Average number of days in a year = 365.25, reflecting the Julian Year of three years with 365 days each and one leap year of 366 days.

IMC-CS4 (LY3022855)

Medical history

Pre-treatment disease characteristics:

- Cancer type
- Initial and current TNM staging
- Pathological confirmation of malignancy
- Sites of Metastatic Disease
- Duration of disease (months from pathological confirmation of malignancy to first dose; if the day of confirmation of malignancy is unknown it will be replaced by 15MMMMYYYY)

Prior anticancer treatments or surgery:

- Type of therapy
- Prior Surgery

Baseline vital signs, physical examination, laboratory assessments, tumor assessments will be included in the tables summarizing these variables across scheduled study visits.

5.3.3 Analysis of Efficacy Data

Efficacy data will be analyzed overall using the Safety population.

5.3.3.1 Response

Best overall response rate (number of subjects who achieve a best response of CR or PR during therapy divided by the total number of subjects treated) and disease control rate (number of subjects who achieve a best response of CR or PR or SD during therapy divided by the total number of subjects treated) will be presented for each cohort of subjects and overall. In addition all tumor assessments will be included in patient listings.

5.3.4 Analyses of Safety Data

5.3.4.1 Study Drug Exposure

The following variables will be summarized according to the definitions provided in section 5.2.1.4. Exposure analyses will include the following:

Cycle 1 only using the MTD population:

- Number of infusions
- Cumulative dose (mg/kg)
- Dose intensity (mg/kg/week)
- ~~Adjusted dose intensity (mg/kg/week)~~
- Relative dose intensity (%)
- Number (%) of subjects with dose modifications (reduced or change of infusion rate).

Across all cycles using the Safety population

- Duration of treatment (weeks)
- Duration of cycles (weeks)
- Number (%) of subjects treated by cycle.
- Number of infusions
- Cumulative dose (mg/kg)
- Dose intensity (mg/kg/week)
- Adjusted dose intensity (mg/kg/week)
- Relative dose intensity (%)
- Number (%) of subjects with dose modifications (reduced or change of infusion rate).

5.3.4.2 Dose Delays and Dose Modifications

The number and percentage of patients with dose delays > 3 days (within Cycle 1 and overall) will be presented. The number and percentage of patients with any dose reduction (reduction to first or second dose level) will also be presented.

IMC-CS4 (LY3022855)

Version 2.0

5.3.4.3 Treatment Emergent Adverse events

Treatment-emergent AEs will be summarized by MedDRA® System Organ Class (SOC) and preferred term (PT), classified from verbatim terms. The incidence and percentage of subjects with at least one occurrence of a preferred term will be included, according to the most severe NCI-CTCAE grade. Causality (relationship to study drug) will be summarized separately. If more than one AE is recorded for a patient within any SOC or PT term, the patient will only be counted once on the most severe grade and the closest relationship to treatment.

AEs reported with a causal relationship of ‘possibly related’ and ‘probably related’ to study medication or ‘does not know’ will be considered related to study medication. Missing classifications concerning study medication relationship will be considered as related to study medication.

The following will be summarized using the Safety population for all AEs, and the MTD population for AEs with onset date in Cycle 1 (ie, within 21 days after last dose in Cycle 1 and prior to start of Cycle 2):

- All AEs,
- SAEs,
- NCI-CTCAE Grade 3 or higher AEs,
- Related AEs, SAEs, and NCI-CTCAE Grade 3 or higher AEs,
- AEs leading to dose modification, study medication discontinuation, and death will be summarized according to MedDRA® Preferred Terms.
- Duration of AE will be determined and included in listings along with action taken and outcome.

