5.1.2 Safety Population

All enrolled subjects who received at least one dose of IMC-CS4 will be included in the Safety Population, regardless of their eligibility for the study. The Safety population will be used for the analysis of baseline characteristics, efficacy data and safety data.

5.1.3 ~~Maximum Tolerated Dose~~Dose Limiting Toxicity

~~(MTD-DLT)~~ Population

Subjects who complete the initial 6 weeks of therapy¹ or experience a DLT during the first cycle will be included in the ~~MTD-DLT~~ Population. Patients who discontinued during the initial 6 weeks due to reasons other than DLT will be excluded from the ~~MTD-DLT~~ population. The ~~MTD-DLT~~ population will be used for the evaluation of DLTs in order to determine the ~~MTDRP2D~~.

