5.2 Definitions and data handling conventions

5.2.1 Safety Data Handling and Definitions

5.2.1.1 Coding

- **Adverse events:** All adverse events (AE) will be coded by the Medical Dictionary for Regulatory Activities (MedDRA™) and graded according to the National Cancer Institute (NCI) Common Terminology Criteria for Adverse Events (CTCAE), Version 4.0 (version 4.0 includes all of the minor versions 4.0x).

¹ i.e. first four infusions completed, plus an observation period of 21 days after last dose in cycle 1 or entry into cycle 2 if start of cycle 2 occurs before completion of the 21 days observation.
IMC-CS4 (LY3022855)

- **Pre treatment Therapy and Concurrent Therapy:** Current medications, medications taken within 30 days prior to first dose of study therapy, prior cancer therapy will be coded using the WHOdrug.

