For analysis of dose exposure **in Cycle 1 only** the same definitions as across all cycles will be used except the following:

- Duration of cycles (in weeks)⁷ = (Date of last dose – date of first dose+21) / 7
Or if start of cycles 2⁸ occurs before last dose of cycle 1 + 21 days:
Duration of cycles (in weeks)= (Date of start Cycle 2-date of first dose)/7

⁵ 14 days is subtracted from the duration of cycle because the 2-week observation period is excluded from the duration of treatment.

⁶ Except in case of weight change from baseline $\geq 10\%$ as described above.

⁷ 21 days added to duration of cycle, because of a 2-week observation period after last dose in Cycle 1 (i.e. 21 days until the next dose).

⁸ Start of Cycle 2 is defined as day of first infusion of Cycle 2.

- Cumulative dose (mg/kg) = Sum of [all administered dosages during cycle 1 (mg) / baseline weight (kg)]

Table 2: General Dose Reduction Guidelines

Cohort	Planned Starting dose	First Reduction	Second Reduction
1	2.5 mg/kg weekly	Discontinue IMC-CS4	-
2	0.3 mg/kg weekly	Discontinue IMC-CS4	-
3	0.6 mg/kg weekly	0.3 mg/kg weekly	Discontinue IMC-CS4
4	1.25 mg/kg every 2 weeks	0.6 mg/kg every 2 weeks	0.3 mg/kg every 2 weeks
5	1.25 mg/kg weekly	0.6 mg/kg weekly	0.3 mg/kg weekly
6	2.5 mg/kg every 2 weeks	1.25 mg/kg every 2 weeks	0.6 mg/kg every 2 weeks

Note: Actual dose levels entered in the CRF will be rounded to the nearest dose level listed in this table (e.g. any IMC-CS4 dose level >5 and < 7.5 mg/kg will be rounded to 5 mg/kg for the purpose of the dose reduction calculation). No dose reductions are allowed after a DLT. In the setting of non-life-threatening reversible Grade ≤ 3 IMC-CS4-related toxicities that do not meet the definition of a DLT, IMC-CS4 may be held (if appropriate in the opinion of the Investigator) for a maximum of 3 weeks, until resolution to Grade < 2 .

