6.3 Planned Safety Tables

Table Number	Table Title	Population
	Dose Exposure	
14.3.1.1	IMC-CS4 Dose Exposure in Cycle 1	DLT
14.3.1.2	IMC-CS4 Dose Exposure	Safety
14.3.2	IMC-CS4 Dose Delays and Modifications in Cycle 1	DLT
14.3.2	IMC-CS4 Dose Delays and Modifications	Safety
	Adverse events	
14.3.5	Summary of Adverse Events	Safety
14.3.6	DLTs by SOC and PT (Cycle 1)	DLT
14.3.7.1	Adverse Events by SOC and PT	Safety
14.3.7.2	Adverse Events by SOC and PT (Cycle 1)	DLT
14.3.8.1	Severe Adverse Events by SOC and PT	Safety
14.3.8.2	Severe Adverse Events by SOC and PT (Cycle 1)	DLT
14.3.9.1	Serious Adverse Events by SOC and PT	Safety
14.3.9.2	Serious Adverse Events by SOC and PT (Cycle 1)	DLT
14.3.10.1	Related Adverse Events by SOC and PT	Safety
14.3.10.2	Related Adverse Events by SOC and PT (Cycle 1)	DLT
14.3.11.1	Related Severe Adverse Events by SOC and PT	Safety
14.3.11.2	Related Severe Adverse Events by SOC and PT (Cycle 1)	DLT
14.3.12.1	Related Serious Adverse Events by SOC and PT	Safety
14.3.12.2	Related Serious Adverse Events by SOC and PT (Cycle 1)	DLT
14.3.13.1	Adverse Events Resulting in Treatment Delay or Modifications by SOC and PT	Safety
14.3.13.2	Adverse Events Resulting in Treatment Delay or Modifications by SOC and PT (Cycle 1)	DLT

14.3.14.1	Adverse Events Resulting in Treatment Discontinuation by SOC and PT	Safety
14.3.14.2	Adverse Events Resulting in Treatment Discontinuation by SOC and PT (Cycle 1)	DLT
14.3.15.1	Adverse Events Resulting in Death by SOC and PT	Safety
14.3.15.2	Adverse Events Resulting in Death by SOC and PT (Cycle 1)	DLT
14.3.16.1	Adverse Events by SOC and PT and Worst Grade	Safety
14.3.16.2	Adverse Events by SOC and PT and Worst Grade (Cycle 1)	DLT
14.3.17	Deaths	Safety
	Physical Examination, Vital Signs, Laboratory Assessments, ECG	
14.3.18	Physical Examination Abnormalities by Scheduled Time	Safety
14.3.19	ECOG Performance Status Shift Table	Safety
14.3.20.3	Vital Signs Shift from Pretreatment to End-of-Study	Safety
14.3.21.1	Vital Signs Shift from Preinfusion to Highest-on-Infusion	Safety
14.3.21.2	Vital Signs Shift from Preinfusion to Lowest-on-Infusion	Safety
14.3.21.3	Vital Signs Shift from Preinfusion to End-of-Infusion	Safety
14.3.22.1	Laboratory CTC Grade Shift from Baseline to Worst Post Baseline Grade- Tests Graded in Single Direction(Either Above or Below Normal Range)	Safety

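### Twelve Cycle 1 safety and exposure tables in the SAP use the MTD/DLT population, so treated subjects who left Cycle 1 without a DLT cannot appear in them

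*SAP*

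**What the plan says.** SAP 5.1.2 defines the Safety population as enrolled subjects with at least one dose, and states: "The Safety population will be used for the analysis of baseline characteristics, efficacy data and safety data".

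SAP 5.1.3 defines a second population, renamed from MTD to DLT, for evaluating DLTs to find the RP2D. It holds subjects who complete the first six weeks or have a Cycle 1 DLT. "Patients who discontinued during the initial 6 weeks due to reasons other than DLT will be excluded" from it.

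The analysis sections then use this second population, under its old name, for more than DLTs. SAP 5.3.4.1 sets the first block of exposure and dose-modification summaries as "Cycle 1 only using the MTD population". SAP 5.3.4.3 summarizes AEs "using the Safety population for all AEs, and the MTD population for AEs with onset date in Cycle 1". SAP 6.3 marks the matching tables DLT in its population column.

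Protocol Version 7.0, sections 12.2 and 12.5.2, confines the DLT population to DLTs and the RP2D and gives every remaining safety analysis to the safety population, meaning all who received any dose.

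**The concern.** The safety profile is a primary objective in both documents, and Cycle 1 is where a reader will look first. Subjects who leave Cycle 1 without a DLT are foreseen: protocol 4.1.1 provides for replacing them. Some will leave because of an AE. Under protocol 4.1.4 an event must be related to IMC-CS4 to be a DLT, so an unrelated AE that ends treatment does not qualify. Protocol 10.2 also lists intolerable, persistent moderate toxicity as a reason for withdrawal.

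Such a subject is dropped from numerator and denominator of every Cycle 1 AE table. The problem is sharpest in Tables 14.3.14.2 and 14.3.15.2. A subject who stops or dies in Cycle 1 from an AE that is not a DLT is removed because of the very outcome the table reports. In the Cycle 1 exposure table, the infusion counts and cumulative doses of these early leavers are missing as well.

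**Working it through.** **Count of tables (SAP 6.3).** Tables 14.3.7.2 to 14.3.16.2 are 10 Cycle 1 AE tables, all marked DLT. Table 14.3.1.1 (Cycle 1 exposure) and the Cycle 1 version of Table 14.3.2 (the number is used twice) are also marked DLT. 10 + 1 + 1 = 12. Table 14.3.6 and Listing 15.1 report DLTs and belong on that population.

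**Who is missing.** Subjects with a DLT stay in, because having one is enough for inclusion under 5.1.3. Completers stay in. Treated subjects who stopped early without a DLT are out.

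**Effect on an AE rate.** The documents give no figure for early stops without a DLT, so every count here is assumed. Let c be retained subjects with a events, and r excluded subjects with b events.

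- Cycle 1 table: a/c. All treated: (a + b)/(c + r).
- Difference, all treated minus table: [r/(c + r)] × (b/r − a/c).
- Take c = 6, a = 1 (a DLT that ended treatment), r = 2. The table shows 1/6 = 16.7% whatever b is.
- b = 0: 1/8 = 12.5%, so the table overstates by 4.2 points.
- b = 1: 2/8 = 25.0%, so it understates by 8.3 points.
- b = 2: 3/8 = 37.5%, so it understates by 20.8 points.

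On a trial-wide scale, assume 72 treated, 4 to 18 early leavers (about 5% to 25%) and an AE in about 20% of those retained. If about 60% of leavers had the AE, the table shows 14/68 = 20.6% to 11/54 = 20.4%, against 16/72 = 22.2% to 22/72 = 30.6% among all treated. If leavers had it at about 20%, the all-treated figure is 15/72 = 20.8% at both ends: the percentage barely moves, but 4 to 18 subjects and their events are absent.

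**Effect on infusion counts.** Cohort 5 plans 4 weekly Cycle 1 infusions of 1.25 mg/kg (protocol Table 1). Assume 3 completers and 2 excluded subjects who left after k infusions.

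- Table mean: 4.0. All treated: (3 × 4 + 2k)/5.
- k = 1, 2, 3, 4 gives 2.8, 3.2, 3.6, 4.0. The table is too high by 43%, 25%, 11%, 0%. Cumulative dose in mg/kg is 1.25 times these means, so the percentages are the same.
- Reverse case: 2 DLT subjects with 1 infusion each, 1 completer, 1 excluded subject with 3 infusions. Table: (1 + 1 + 4)/3 = 2.0. All treated: (1 + 1 + 4 + 3)/4 = 2.25. The table is 11% too low.

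**Relative dose intensity (SAP 5.2.1.4).** For a subject who stops in Cycle 1, treatment duration in weeks is (last dose date − first dose date + 7)/7. After k uninterrupted weekly infusions this is [7(k − 1) + 7]/7 = k weeks. Dose intensity is 1.25k/k = 1.25 mg/kg/week, so relative dose intensity is 100% for any k. A completer who goes on to Cycle 2 has (21 + 21)/7 − 2 = 4 weeks and 5.0/4 = 1.25 mg/kg/week, also 100%. Leaving out early stoppers without a gap therefore does not shift this measure.

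**The case against.** The strongest reply is that the Cycle 1 set is a deliberate extra view, laid beside the DLT table on the same subjects. Each Cycle 1 AE table has an all-cycle partner on the Safety population (14.3.7.1 to 14.3.16.1). All-cycle exposure, the deaths table (14.3.17) and the AE listings are also on Safety. No event is lost from the report, and no dose decision is shown to depend on the Cycle 1 tables. This stands, and it limits the scope. It does not repair Cycle 1 tables of discontinuations and deaths that leave out such events by definition.

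A reader might infer four stronger things that the documents do not support.

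- *That the SAP flatly contradicts itself.* SAP 5.1.2 assigns safety data to the Safety population but does not say exclusively. The exclusive wording is in protocol Version 7.0.
- *That the SAP departed from its protocol without declaring it.* SAP 3.1 ties the plan to protocol Version 3.0 of 28 March 2012, whose text is not available. The entry of no changes in SAP 5.5 therefore cannot be tested. The Version 7.0 change log covers only changes from Version 6.0, so its silence on 12.2 and 12.5.2 says nothing about Version 3.0.
- *That Cycle 1 dose intensity is generally flattered.* The formula gives 100% to an early leaver with no gap.
- *That a missed infusion also removes a subject.* The footnote to 5.1.3 describes completion as "first four infusions completed, plus an observation period of 21 days after last dose in cycle 1", and the note to SAP Table 2 says that for "toxicities that do not meet the definition of a DLT, IMC-CS4 may be held". But the footnote cannot be a literal general rule, since Cohort 4 has only two Cycle 1 infusions, and a held dose given later may still leave four completed. Losses from Table 14.3.13.2 (AEs leading to delay or modification) are not established.

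**Conclusion.** The point holds for the twelve tables. AEs of treated subjects who left Cycle 1 without a DLT cannot appear in the ten Cycle 1 AE tables. In Tables 14.3.14.2 and 14.3.15.2 the omission is tied to the outcome itself. Cycle 1 infusion counts and cumulative dose leave out the same subjects. The assignment fits poorly with SAP 5.1.2 and departs from current protocol 12.2 and 12.5.2, with the reservation that part of this may be a version gap.

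The size and direction are unknown. The AE rate is understated only if excluded subjects have the higher rate, and the infusion count can err either way. The figures rest on assumed counts and show what could happen, not what did. The damage is confined to the Cycle 1 tables.

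**What to change.** - SAP 5.3.4.1: put the Cycle 1 exposure and dose-modification summaries on the Safety population.
- SAP 5.3.4.3: summarize AEs with Cycle 1 onset on the Safety population, with all treated subjects in the cohort as denominator.
- SAP 6.3: change DLT to Safety for Table 14.3.1.1, the Cycle 1 version of Table 14.3.2, and Tables 14.3.7.2 to 14.3.16.2.
- Keep the DLT population for SAP 5.3.4.4, Table 14.3.6 and Listing 15.1.
- If DLT-population versions of the Cycle 1 tables are still wanted, label them supplementary.

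The cost is a population label in three SAP sections and twelve table shells. No new data are needed, and SAP 5.2.1.4 already has a duration formula for subjects who stop in Cycle 1.
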